Sample Size and Power: The goal of this pilot study is to estimate the cessation rates in each arm to obtain an effect size for future larger studies. To conduct a hypothesis test for the comparison of cessation rates between the two intervention arms will require a minimum 199 people in each arm (total sample=398) for at least 80% power. This calculation was based on a 2-sided test with the type I error of 0.05, and assuming a 20% cessation rate in the *Sense2Quit App* group (intervention) and a 10% cessation rate in the control arm. The 10% difference would be equivalent to a medium effect size (Cohen's $d=0.45$). In this pilot study, we propose a total sample of 60 (30 per group) of whom we expect there to be 20% attrition. Therefore, this study is not powered to detect a significant difference between study arms. Instead, for the sample size (30 per group), this study will have at least 80% probability that the standard error of the cessation rate estimates $\leq 7\%$. We assume that the expected cessation rates range from 10% to 20%, and therefore the sample size is sufficient to provide a power estimation for a larger trial with acceptable reliability.

Recruitment and Retention: Strategies for recruitment and retention are described in the Recruitment and Retention attachment. We will enroll 60 PLWH who smoke tobacco. Inclusion/exclusion criteria are described above.

Screening: Potential study participants will provide verbal informed consent by phone or complete an eConsent form through REDCap prior to completing a phone screening process that assesses eligibility. If eligible, participants will attend a baseline session described below.

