Data Analysis: This is a pilot study to assess preliminary feasibility, acceptability, and efficacy. Descriptive statistics will be used for all analyses. The rate of quit attempts will be calculated as the proportion of smokers who attempt to quit (i.e., no smoking during a 24 hours period); 7-day point prevalence abstinence will be calculated as the proportion of smokers who are biochemically verified (saliva cotinine) 7-day abstinence at a given time point; and sustained abstinence will be calculated as proportion of days of no smoking starting on the quit date among those who attempt to quit. We will provide point estimates and corresponding confidence intervals of these measures for each arm. Because of our small sample sizes, we will obtain Clopper-Pearson exact confidence intervals based on the binomial distribution. Given the small sample size, the purpose of the arms is to monitor for unexpected, gross differences between the two groups. To determine acceptability, we will ask participants in both arms how useful each of the intervention components were (1 = *Not at all useful* to 7 = *Extremely useful*) and whether they would recommend the program to a friend (1 = *Definitely would not recommend* to 7 = *Definitely would recommend*). For the intervention to be deemed acceptable, the mean level for each of these measures would have to be five or

higher. The efficacy of the intervention will be based on saliva- confirmed 7-day point prevalence abstinence at the final study visit. Lost-to-follow-up participants will be included as smokers.

NOT-OD-15-102: Consideration of Sex as a Biological Variable: In accordance with NIH guidance, we will include sex as a biological variable in the study design (enroll equal numbers of males and females), analyses, and reporting. We will report all primary and secondary outcomes separately by sex to enhance rigor and transparency of our findings in addition to including sex in all multivariate models.

AIM 3: Employ the RE-AIM framework to assess the potential scale-up of the *Sense2Quit App*.

In addition to testing the Efficacy of the *Sense2Quit App*, we will concurrently measure the four remaining RE-AIM dimensions⁸⁸ as follows:

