Statistical Design and Data Analysis: This is a pilot study to assess preliminary feasibility, acceptability, and preliminary efficacy. Descriptive statistics will be used for all analyses. The rate of quit attempts will be calculated as the proportion of smokers who attempt to quit (i.e., no smoking during a 24-hour period); 7-day point prevalence abstinence will be calculated as the proportion of smokers who are biochemically verified 7-day abstinence at a given time point; and sustained abstinence will be calculated as proportion of days of no smoking starting on the quit date among those who attempt to quit. We will provide point estimates and corresponding confidence intervals of these measures for each arm. Because of small sample sizes, we will obtain Clopper-Pearson exact confidence intervals based on the binomial distribution. Given the small sample size, the purpose of the arms is simply to monitor for unexpected, gross differences between the two groups. To determine acceptability, we will ask participants in both arms how useful each of the intervention components were (1 = *Not at all useful* to 7 = *Extremely useful*) and whether they would recommend the program to a friend (1 = *Definitely would not recommend* to 7 = *Definitely would recommend*). For the intervention to be deemed acceptable, the mean level for each of these measures would have to be 5 or higher. The efficacy of the intervention will be based on saliva-confirmed 7-day point prevalence abstinence at the follow-up survey. Lost-to-follow-up participants will be included as smokers.

DISSEMINATION PLAN

Tools developed and evaluated during this project have the potential to extend the impact and reach of tobacco cessation for all smokers but specifically for persons living with HIV (PLWH) who smoke. Per the RFA, this study was designed for dissemination (e.g., feasibility/acceptability of the intervention for PLWH) and suitable for the intended context.

Therefore, a multi-faceted dissemination plan targeting various stakeholders is proposed. We will disseminate our findings to technology-oriented and clinical management-oriented audiences. For technology audiences, we will provide enough detail to enable the *Sense2Quit App* to be constructed and used within an appropriate context.

We propose the following dissemination strategies:

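### The binomial interval is the only one named, and it does not fit sustained abstinence, which is a proportion of days and not of people (a descriptive, non-primary measure)

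*Combined protocol and SAP*

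**What the plan says.** The Data Analysis paragraph under Aim 2 defines three measures. The quit-attempt rate and 7-day point prevalence abstinence are each a proportion of smokers. The third is different in kind: "sustained abstinence will be calculated as proportion of days of no smoking starting on the quit date among those who attempt to quit".

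The text then commits to intervals for all three: "We will provide point estimates and corresponding confidence intervals of these measures for each arm". The only method given follows: "Because of our small sample sizes, we will obtain Clopper-Pearson exact confidence intervals based on the binomial distribution". Statistical Design and Data Analysis, under Statistical Design and Power, repeats the definition and the method almost word for word. No other interval method appears anywhere in the document.

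Four other places bear on the measure:

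- **Status.** Operationalization of Outcome Measures makes cotinine-validated 7-day abstinence the primary efficacy outcome. All analyses are described as descriptive.
- **Table 3.** Under tobacco cessation it lists a count of continuously abstinent days. That is not the same quantity as the share of smoke-free days.
- **Quit date.** The Overview sets it at the baseline visit. The Aim 2 Procedures allow baseline or a date up to about a week later. Both statements sit in text on the intervention arm, and no section expressly gives control participants a quit date.
- **Loss to follow-up.** "Lost-to-follow-up participants will be included as smokers". This is a rule for participants. It does not say how days are counted.

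**The concern.** Clopper-Pearson needs a count of independent yes/no units. A proportion of days supplies one on neither natural reading.

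- **People as the unit.** The plan's stated reason, small samples, points this way. Each attempter then contributes a fraction of days, the arm figure is a mean of fractions, and the method has no count to work on.
- **Days as the unit.** Pooling gives a count out of roughly two thousand days, so the calculation runs. But a person who abstains on one day is likely to abstain on the next, and the interval treats all those days as independent.

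Only the second reading yields a number directly, and that number overstates precision badly. An interval about 2 points either side, from some two dozen people, could make chance variation look like the kind of gross difference between arms that the analysis is meant to spot.

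**Working it through.** **Plan's own figure.** There is none for this measure. The 199 per arm in Sample Size and Power concerns cessation rates and does not enter here.

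**Inputs**

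- Attempters per arm: *m* = 24. This is 30 per arm less the 20% attrition in Sample Size and Power (30 × 0.8 = 24), and it assumes that all who remain attempt to quit.
- Days per person: *D* = 84, from 12 weeks of follow-up (12 × 7), assuming a complete daily record.
- Mean share of smoke-free days: *p* = 0.40. Assumed.
- Within-person correlation of days (ICC): 0.05, 0.2, 0.5. Assumed; the documents give no value.
- Confidence level: 95%. Assumed; the plan states none for its intervals.

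**People as the unit.** 24 × 0.40 = 9.6, which is not a count. Clopper-Pearson is undefined here unless some rounding is invented, and the plan proposes none.

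**Days pooled.** 24 × 84 = 2,016 days, of which 40% is about 806. Clopper-Pearson on 806/2,016 gives 37.8% to 42.2%, a half-width of about 2.2 points. The normal approximation agrees: 1.96 × √(0.4 × 0.6 / 2,016) = 0.021.

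**Effect of correlation.** The variance of the arm figure is inflated by DE = 1 + (84 − 1) × ICC. The pooled interval ignores this, so its coverage is about 2Φ(1.96/√DE) − 1. A person-level t interval has half-width of about 2.069 × √(0.24 × DE / 2,016), where 2.069 is the 97.5% point of t on 23 degrees of freedom.

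| ICC | DE | Pooled coverage, formula | Pooled coverage, simulated | Person-level t half-width, formula | Person-level t coverage, simulated |
|---|---|---|---|---|---|
| 0.05 | 5.15 | 61% | about 62% | 5.1 points | 95% |
| 0.2 | 17.6 | 36% | 36–37% | 9.5 points | 95% |
| 0.5 | 42.5 | 24% | 24–25% | 14.7 points | 95% |

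The simulations draw beta-binomial days with 20,000 runs per row. Mean simulated t half-widths were 5.1, 9.4 and 14.7 points; the pooled half-width stayed between 2.1 and 2.2 throughout.

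**Check on the model.** Someone who attempted to quit should normally have at least one smoke-free day, but the model can generate people with none: about 0%, 0.4% and 11% of people in the three rows. With those people removed, pooled coverage is 63%, 36% and 25%, and the t half-width is 5.1, 9.4 and 14.2 points. The conclusion does not move. At an ICC of 0.8 the share with none is 37%, and removing them lifts the attempters' mean from 40% to 64%. That setting is therefore left out of the table, although pooled coverage there is still only 19–21%.

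**Start day.** Someone who smokes for the first 7 of 84 days and then stops scores 77/84 = 92% counted from baseline and 100% counted from day 7. The choice of start day can move an individual's value by 8 points.

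**The case against.** The strongest reply is that nothing rests on this interval. The measure is descriptive and not primary, no test or decision rule uses it, and the planning purpose concerns something else: "The goal of this pilot study is to estimate the cessation rates in each arm to obtain an effect size for future larger studies". That stands, and it is why the point is minor.

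A second reply is that Clopper-Pearson was meant only for the two binary measures. In that case sustained abstinence has a promised interval and no method, and the same sentence repairs it. A third is that the authors may intend a yes/no status per person, which the method would fit. The written definition does not say that, but adopting it would be a sound remedy.

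Three stronger readings are tempting, and the documents do not support them:

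- *That the trial's intervals are wrong in general.* They are not. The primary outcome and the quit-attempt rate are counts of people.
- *That the sponsor will pool days.* The unit is not stated, and the appeal to small samples points to people.
- *That restricting to attempters, a subset formed after randomisation, makes the figure unusable.* The restriction is disclosed. The arms are there only so that "the purpose of the arms is to monitor for unexpected, gross differences between the two groups". The quit-attempt rate per arm is also reported. If non-attempters score zero, the all-randomised mean is the product of the two figures: 60% attempting with 40% smoke-free days, and 80% attempting with 30%, both give 24%. A difference in attempting is therefore already visible.

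**Conclusion.** The point holds and is minor. For one of three measures the only interval method named cannot be applied as written. On the one reading where it can be computed, it is far too narrow: a half-width of about 2 points where about 5 to 15 is warranted, with coverage of about 62% down to 24–25% instead of 95%. The sizes depend on assumed values for the number of attempters, days, smoke-free share and correlation. The direction depends only on days within a person being positively correlated. The mismatch itself needs no assumption, since it follows from the definition and the method as written. The primary outcome, the quit-attempt rate and the sample size are unaffected.

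**What to change.** In both analysis paragraphs, limit Clopper-Pearson to quit attempts and 7-day abstinence. Then choose one of two routes for sustained abstinence:

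1. **Keep it as a share of days.** For example: *For each participant who attempts to quit, the percentage of smoke-free days from the start day will be computed; the arm mean will be reported with a person-level interval (t or bootstrap) and labelled descriptive.* The choice between t and bootstrap is a preference.
2. **Redefine it as yes/no per person**, with the condition spelled out. Clopper-Pearson then fits.

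Whichever is chosen, reconcile the measure with the continuous-abstinence entry in Table 3. Reconcile the quit-date statements in the Overview and the Aim 2 Procedures, and use one start-day definition for this measure in both arms. State how days after loss to follow-up are counted. A mean over all randomised participants is optional.

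The cost in text is a few sentences. There are two drawbacks. The interval will be wider than the pooled one, and it is only approximate with few attempters. It also should not be assumed that the data already exist. The Procedures describe a 30-day timeline follow-back at baseline, visits at weeks 4 and 12, and weekly check-in calls with no stated daily count; passive app data exist only in the intervention arm. If a 30-day look-back were repeated at week 12 (an assumption), 56 − 30 = 26 of the days after week 4 would be uncovered. The sponsor should confirm the daily record in both arms before choosing the first route.

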
AIM 1: Explore and identify, using qualitative methods, acceptable and appropriate app content and features of the *Sense2Quit App* to support smoking cessation and relapse prevention in PLWH who smoke. We will conduct focus groups, design sessions, and usability assessments with HIV-positive daily smokers, former smokers, and usability experts. This feedback will guide tailoring of the app to this population of smokers.

AIM 2: Conduct a pilot randomized controlled trial to examine the feasibility, acceptability, and preliminary efficacy of the *Sense2Quit App*. We will randomize 60 HIV-positive smokers to the *Sense2Quit App* plus the Fossil Gen5E smartwatch, standard smoking cessation counseling, and nicotine replacement therapy (active condition) versus

standard smoking cessation counseling plus referral to NYC Quitline (control) in order to examine group differences in rate of quit attempts, 7-day point prevalence abstinence, and sustained abstinence.

AIM 3: Employ the RE-AIM framework to assess the potential scale-up of the *Sense2Quit App*.

IMPACT: Given the high rates of tobacco use among PLWH, the Sense2Quit App has considerable potential for reducing morbidity and mortality among PLWH who smoke.

AIM 4: Testing with Confounding Gestures. To improve the accuracy of smartwatch smoking detection within the current version of the app, we will perform additional testing on the smartwatch with participants who will complete a set of hand gestures to distinguish them from smoking gestures.

STUDY TIMELINE

We will implement a 2-year timeline to accomplish study specific aims. The details of the study activities, including development of the *Sense2Quit App* and the detailed timeline for the clinical trial, are listed in **Table 1**.

Table 1.

Timing (Year/Month)	Enrollment Target	Milestones
Year 1	“Just in Time” 1-3	
 Protocol & manual of procedures finalized Institutional Review Board (IRB) approvals Recruitment: Pre-screen potential participants, contact participants from database, advertisements/brochures in local clinics, provider meetings, presentations to community groups about study
		
 Aim 1 – Focus Group Sessions Coding of qualitative data begins
		
 Aim 1 – Design Sessions Code and analyze qualitative data

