A research study involving a mobile technology intervention for persons living with HIV (PLWH). The research activities will take place in New York City, and data collection will take place at Columbia University. Participants will be recruited online and offline through social networking websites and apps and through local community-based

Figure 2. (a) Visual reminders, (b) Motivational messages will be

organizations, health centers, and local events. The study will test the *Sense2Quit App* for smokers living with HIV.

Participants in the intervention arm will receive Nicotine replacement therapy (NRT). Participants will be provided with an 8- week supply of combination NRT that they will begin after the baseline visit. The quit date will be the date of their baseline visit. Participants will be offered all 3 forms of NRT (patch, lozenge, gum) and will be allowed to choose 2 forms (combination: patch/lozenge or patch/gum) to use.

Participants who smoke 10 or more cigarettes per day will receive the following dosage for their NRT patch: one 21 milligram patch per day for 4 weeks; one 14 milligram patch per day for 2 weeks; and one 7 milligram patch per day for 2 weeks. Participants who smoke less than 10 cigarettes per day will receive the following dosage: one 14 milligram patch per day for 6 weeks and one 7 milligram patch per day for 2 weeks. This is considered the standard clinical treatment, and participants will receive additional instructions on usage of the patch. Participants will be told the risks of using the patch, which include skin irritation, itching, dizziness, headache, rapid heartbeat, and nausea. Participants will also be advised that they can curb additional cravings with their choice of Nicotine gum or lozenge available for purchase over-the-counter.

Setting. The study will be conducted at Columbia University which provides HIV care for a diverse group of more than 2,000 PLWH. A recruitment plan, which outlines how participants will be recruited through the clinic and community-based organizations, is outlined below.

Participants.

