Inclusion criteria: For Aim 1, (1) PLWH; (2) ≥ 18 years of age; (3) current or former smoker (where smoking is defined as ≥ 5 cigarettes a day for the past 30 days, past smoker is defined as having at one point smoked a minimum of ≥ 5 cigarettes per day for a period of at least 30 days) and (4) understand and read English; Aims 2 and 3 follow the same inclusion criteria with the added criteria that (1) PLWH will be confirmed through medical records or pill bottles for ART medications; (2) only current smokers are eligible (where smoking is defined as ≥ 5 cigarettes a day for the past 30 days); (3) own an Android smartphone (if they do not have a phone compatible with the app, they will be provided with one to use during the study); (4) not pregnant or breastfeeding (due to contraindications for Nicotine Replacement Therapy [NRT]); (5) permanent contact information; (6) interested in quitting smoking within 30 days; and (7) blows ≥ 5 CO into a breath analyzer at baseline. For Aim 4) participants will be PWH who smoke cigarettes and will either be 1) enrolled participants at their 12-week follow-up visit; 2) participants who are initially eligible for the study after completing the screener but do not qualify based on eCO levels; or 3) participants who already finished Aim 2 (and 3, if applicable).

Exclusion criteria. For Aim 1, participants will be excluded if they do not meet the defined inclusion criteria. For Aims 2 and 3, the exclusion criteria will be (1) use tobacco products other than cigarettes (i.e., cigars, piped tobacco, chew, snuff); (2) planning to move within 6 months of enrollment; (3) alcohol dependence measured through the AUDIT-C⁶⁰; (4) positive history of a medical condition that precludes nicotine patch use; (5) current use of NRT or other smoking cessation medications (e.g., Chantix or Zyban); (6) current enrollment in another smoking cessation program; and (7) household member is also participating in the Sense2Quit study (due to study contamination). For Aim 4, participants will be excluded if they fail to meet the inclusion criteria.

Inclusion of Individuals

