Participants will be offered all 3 forms of NRT (patch, lozenge, gum) and will be allowed to choose 2 forms (combination: patch/lozenge or patch/gum) to use. Also for those in the intervention arm, study staff will provide participants with a Fossil Gen5E or Tic Watch smartwatch and initiate the *Sense2Quit App* on the participant's smartphone. If a participant's smartphone is not compatible with the *Sense2Quit* app, they will be provided with a smartphone to be used during the 12-week long study.

The *Sense2Quit App* will passively collect smoking data, such as when the user smokes (time of day, day of week, before/after eating, after waking up/before going to sleep, before driving to/from work, while driving), where the user smokes, and who is nearby. The *Sense2Quit App* will provide real-time feedback to participants, providing them with tips and messages to urge them to quit smoking when they lift their hand up for a smoke. The *Sense2Quit App* will be paired with the smartwatch so that smoking will be detected by the smartwatch and will be sent directly to the App. The *Sense2Quit App* will reliably predict cravings, target users with notifications to prevent individuals from smoking, refine notifications for each user, and display their change in smoking behavior in a smoking graph and money spent in a cash spent graph. Users will also be able to see their quit plan with their assigned quit date which will be baseline or another set date within a short period after baseline (i.e. within a week of completing the baseline visit), along with smoking trends, supporting tips, videos and games. The study staff member will show the participant how to use the app, and will also help them set up a reminder to take their daily HIV medication and use NRT at their baseline appointment. Participants will wear the smartwatch and

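### Sustained abstinence is compared between arms only among participants who attempt to quit, a post-randomization group the intervention may change, so the contrast can mislead about size or sign

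*Combined protocol and SAP*

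**What the plan says.** The definition appears in the same words in AIM 2, Data Analysis and in STATISTICAL DESIGN AND POWER, Statistical Design and Data Analysis: "sustained abstinence will be calculated as proportion of days of no smoking starting on the quit date among those who attempt to quit". Both sections describe the quit-attempt rate in nearly the same terms, in AIM 2 as the "proportion of smokers who attempt to quit (i.e., no smoking during a 24 hours period"). One smoke-free 24-hour period is therefore enough to enter the denominator.

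The Aim 2 statement in SPECIFIC AIMS says the randomized arms exist to "examine group differences in rate of quit attempts, 7-day point prevalence abstinence, and sustained abstinence". Quit attempts thus serve both as an outcome and as the entry condition for another outcome.

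According to AIM 2, Procedures, the app works by "providing them with tips and messages to urge them to quit smoking when they lift their hand up for a smoke". The intervention arm also receives a supply of nicotine replacement, while controls are referred to the Quitline, through which they can obtain it.

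No section gives a version of sustained abstinence for everyone randomized. The Data Safety and Monitoring Plan mentions intent-to-treat analysis only in general terms.

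**The concern.** Randomization makes the two groups of 30 comparable. It does not make the two groups of attempters comparable, because who attempts is decided afterwards and may depend on the arm. Suppose the app and nicotine replacement bring in some smokers who would not have managed a smoke-free day as controls. In the app arm they enter the average, possibly with few smoke-free days. Their counterparts in the control arm are left out. The app arm's average then falls even though smoke-free days have been added.

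The direction is not fixed. If the extra attempters did better than the rest, the attempter-only contrast would move upward and suggest more durable abstinence, although nobody who would have attempted anyway had improved.

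The analysis sections say the arms are there to show large, unexpected differences. A contrast that can create or hide a gap through its denominator serves that purpose poorly, even when no test is planned.

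**Working it through.** **Plan's own figures.** The documents give no number for sustained abstinence or for the attempt rate. The one reproducible planning figure is 199 per group, for 20% versus 10% cessation, two-sided 0.05, 80% power. With pooled variance: (1.960 × √(2 × 0.15 × 0.85) + 0.842 × √(0.16 + 0.09))² / 0.10² = 199. It rests on cessation, not on sustained abstinence.

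**Inputs.** From the documents: 30 per arm; an attempt is at least one smoke-free 24-hour period. Assumed: the numbers of attempters and their shares of smoke-free days.

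**Formulas.** Let *a* core attempters in each arm average *c* percent smoke-free days. Let *e* extra attempters, in the app arm only, average *x* percent. Let *g* be any gain the app gives core attempters, in points. A non-attempter has no smoke-free 24-hour period and so scores 0. Each figure is taken as a mean of per-person proportions. App minus control is then:

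- attempters only: [a·g + e·(x − c)] / (a + e)
- all randomized: [a·g + e·x] / 30

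With g = 0, the first is negative whenever x is below c, and the second is positive whenever x is above 0.

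**No gain among core attempters (c = 40, x = 15, g = 0).**

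| Attempters of 30, control vs app | Attempters only, app vs control | Difference | All randomized, app vs control | Difference |
|---|---|---|---|---|
| 15 vs 27 | (15×40 + 12×15)/27 = 28.9% vs 40.0% | -11.1 | 780/30 = 26.0% vs 600/30 = 20.0% | +6.0 |
| 27 vs 30 | (27×40 + 3×15)/30 = 37.5% vs 40.0% | -2.5 | 1125/30 = 37.5% vs 1080/30 = 36.0% | +1.5 |

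In the second row a core gain of g = 3×25/27 = 2.8 points brings the attempter-only difference to zero.

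**A real gain among core attempters (c = 50, x = 20, g = 5).**

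- 18 vs 24 attempters: attempters only (18×5 − 6×30)/24 = -3.75 points; all randomized (18×5 + 6×20)/30 = +7.0.
- 27 vs 30 attempters: attempters only (27×5 − 3×30)/30 = +1.5 points; all randomized (27×5 + 3×20)/30 = +6.5. The sign holds, but the size is understated.

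**No distortion.** With e = 0 and the same kinds of people attempting in both arms, the attempter-only contrast equals g. Equal attempt rates alone are not enough if different people make up the attempters.

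**The case against.** Four points on the other side carry weight.

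**The outcome is minor.** The primary efficacy outcome is cotinine-validated 7-day abstinence, with people lost to follow-up counted as smokers, and it is not limited to attempters. All analyses are descriptive. This stands and limits the importance of the point.

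**The missing piece is reported alongside.** The attempt rate is given for each arm, and attempt rate times attempter mean gives the all-randomized mean: 27/30 × 28.9% = 26.0% and 15/30 × 40% = 20.0%. A careful reader could recover it. However, the plan neither forms this product nor gives an interval for it, while Aim 2 names sustained abstinence itself as a group comparison.

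**Attempt rates may be high in both arms.** Participants must be "interested in quitting smoking within 30 days". Both arms receive counselling and weekly calls, controls can obtain nicotine replacement through the Quitline, and one smoke-free day counts as an attempt. The 27 versus 30 case may therefore be closer to what happens than 15 versus 27. The protocol guarantees neither.

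**Durability among attempters is a fair question.** A stated purpose of the app is to keep a slip from becoming a relapse. As a within-arm description the figure is useful; the difficulty lies in using it to compare arms.

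A reader might also infer that a misleading value would carry into the planned larger trial. The documents do not support that. Both sample-size sections take cessation rates as the planning quantity, and no section uses sustained abstinence to judge efficacy or size a trial.

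**Conclusion.** The point holds as a modest one about a denominator. The between-arm contrast in sustained abstinence conditions on a post-randomization outcome and is not protected by randomization. Under the 40% and 15% assumptions with no core gain, the attempter-only difference runs from -2.5 to -11.1 points where the all-randomized difference is +1.5 to +6.0. These are illustrations, not forecasts, because the documents supply no attempt rates or shares of smoke-free days. The negative direction rests on extra attempters doing worse than core attempters.

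It would go too far to conclude that the pilot will report harm from the app. Reversal needs enough extra, weaker attempters to outweigh any gain among the rest, and nothing in the documents shows that this will occur.

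**What to change.** In both analysis sections, define the between-arm figure as the mean proportion of smoke-free days among all participants randomized to each arm, with non-attempters scored 0. Keep the attempter-only figure, labelled as a description within each arm. Two rules have to be written with it.

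- **Start of the day count.** APPROACH, Overview says "The quit date will be the date of their baseline visit", while AIM 2, Procedures also allows a set date within about a week. Both statements stand mainly in text about the intervention arm. They should be reconciled, and the count should start from one date defined the same way in both arms.
- **Unobserved days.** The plan expects 20% attrition, about 6 of 30 per arm (0.20 × 30). Scoring non-attempters 0 does not cover people whose status is unknown or attempters with missing days. Counting unobserved days after loss to follow-up as smoking days would follow the plan's existing smoker rule, which is not currently stated for day counts. A sensitivity analysis can use observed days only.

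The cost is lower reported percentages, because everyone randomized is in the denominator, and a stated missing-days rule. The change uses the day-level smoking data that the planned figure already needs.
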